Study Design	
This is a phase 1, open-label study to determine the pharmacologically active dose range of APR-246 in combination with venetoclax and rituximab in patients with Richter's Transformed NHL (RT) and to select a recommended dose for further development. The study includes a dose escalation design (Figure 1). It is preceded by a brief APR-246 monotherapy lead-in to establish a baseline pharmacokinetic (PK) / pharmacodynamic (PD) profile after intravenous (IV) dosing in each patient and to obtain APR-246 PK after a single dose of APR-246 administered orally (PO). The recommended dose will be based on the safety, tolerability, PK and PD profile of APR-246 in combination with venetoclax and rituximab therapy in patients with RT. Once the recommended dose of APR-246 in combination with venetoclax and rituximab is established, further explorations in expansion arms may be pursued following a protocol amendment.
 
Patients with RT will receive APR-246 administered IV at the assigned cohort dose with standard doses of venetoclax and rituximab. Dose escalation will proceed in a standard 3 + 3 dose escalation design.
 <pre>graph TD; A[Monotherapy Lead-In: D1-7 APR-246 IV Dose X: D1 APR-246 500 mg PO: D2] --> B[Cycle 1: D1-35 APR-246 IV Dose X D1, 8, 15 Venetoclax PO Ramp Up]; B --> C[Cycle 2 and beyond: D1-28 APR-246 IV Dose X D1, 8, 15 Venetoclax PO 400 mg/day Rituximab 375 mg/m² (Day 2 Cycle 2), 500 mg/m² Day 2 Cycles 3-7]; C --- X[X = assigned cohort dose]</pre>

Figure 1: Clinical Trial Schema

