	
APR-246 PO on Day 2. The primary purpose of the monotherapy cycle is to obtain peripheral blood for monotherapy PK and PD analyses following IV and PO administration of APR-246.
 
Patients will start treatment with APR-246 IV as a single agent administered on Day 1 of a single 7-day monotherapy cycle at the assigned cohort dose level, prior to Cycle 1 Day 1 of combination therapy. On Day 2 of the 7-day monotherapy lead-in period, patients will receive a single dose of APR-246 administered PO at the dose of 500 mg. After review of oral PK data from at least 6 patients, a decision can be made whether to increase the PO dose of APR-246 and/or administer APR-246 with a standard high-fat meal to investigate, respectively, dose linearity in PK and/or the effect of food on oral absorption of APR-246. Dose escalation of the oral dose or switching to administration with food will be determined by PK to ensure that the APR-246 exposure levels after oral dosing do not exceed the exposure levels after IV administration in terms of C_{max} and AUC.
 
Combination Treatment
 
After the APR-246 monotherapy lead-in, study treatment will consist of APR-246 administered as an IV infusion, at the same assigned dose that was used during the monotherapy lead-in period, once weekly, on Days 1, 8 and 15 of each cycle, concurrently with venetoclax for the 5-week ramp-up at the dose of 20 mg during Week 1, 50 mg during Week 2, 100 mg during Week 3, 200 mg during Week 4, and 400 mg during Week 5. Beginning Cycle 2 Day 1, venetoclax will be administered at 400 mg (or tolerable dose following 5-week ramp up) PO daily. IV rituximab will be initiated at 375 mg/m² on Cycle 2, Day 2 and then administered at 500 mg/m² on Day 2 of Cycles 3-7. After 6 cycles of treatment with APR-246 in combination with venetoclax + rituximab, APR-246 + venetoclax will continue to be administered starting at Cycle 8 for up to a total of 24 cycles. The safety assessment (DLT) period will occur in the monotherapy lead-in and throughout Cycles 1, 2, and 3 of combination treatment.
 
Patients with RT will receive APR-246 administered IV as the assigned cohort dose with standard doses of venetoclax and rituximab. Dose escalation will proceed in a standard 3 + 3 dose escalation design.
 
Patients who miss >25% of APR-246 doses for a nonmedical reason (patient's preference) or noncompliance will be replaced.
 
Patients who receive at least 3 cycles of study treatment at the assigned dose of APR-246 may proceed to the next dose level of APR-246 that has been demonstrated as safe and tolerable by the DRT in at least 3 patients, provided the dose increase is considered to be in the patient's best interest by the Investigator.
 
Responses will be assessed according to response criteria for RT (Appendix V) via blood, BM, and imaging (positron emission tomography [PET]/computed tomography [CT]). Response assessments are to be performed every 3 cycles and PET-CT scanning is recommended. For patients who achieve CR, imaging may be omitted, and minimal residual disease (MRD) assessment will be completed using flow cytometry and/or molecular techniques from the BM and/or peripheral blood.

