	
Definition of DLT
 
All TEAEs are relevant to the determination of DLTs unless they are clearly and solely due to the disease under study. The DLT evaluation period will be up to 91 days (7 days of APR-246 monotherapy plus 84 days for Cycle 1-3 with combination therapy) after the first dose of APR-246 is administered. A DLT is defined as any of the following TEAEs using the National Cancer Institute Common Terminology Criteria for Adverse Events (NCI-CTCAE), as follows:
 
• Any neurologic toxicity of grade 4• Any grade ≥ 3 non-hematologic toxicity except for:
• First occurrence of grade 3 electrolyte abnormalities and/or creatinine CL decrease resolving to grade 2 (or baseline if baseline is grade ≥ 2) within 48 hours with supportive treatment.• Grade 3 fatigue, nausea, vomiting, diarrhea or other manageable constitutional symptom(s) that is/are responsive to supportive therapy.• Grade 3 infection responding to appropriate antimicrobial therapy.• Any neurologic toxicity of grade 3 that does not return to grade ≤ 1 or baseline within 7 days.• Any grade ≥ 3 hematologic toxicity will be considered a DLT except for:
• Grade 3 neutropenia without fever• Grade 4 neutropenia without fever lasting 8 days or less• Grade 3 thrombocytopenia that does not result in bleeding or transfusion• Grade 3/4 lymphopenia/lymphocytosis• Grade 3/4 white blood cell (WBC) decreased• Grade 3/4 WBC increased 
Any toxicity, regardless of the NCI-CTCAE v5.0 grade, resulting in discontinuation, dose reduction or treatment with less than 75% of planned doses of APR-246 study drug, will be reviewed by the DRT, and will be considered a DLT unless clearly and solely related to the disease under study. The DRT will consist of the Medical Monitor, Site Principal Investigators, and other clinical research personnel that the Sponsor may deem appropriate.
 
G-CSF support for the management of neutropenia and prophylactic antimicrobial therapy are allowed, including during the DLT period.
 
TEAEs that meet the above criteria but that occur after the DLT evaluation period will not be defined as DLTs and will be reported as AEs/SAEs and will be reviewed across all cohorts during the study to help determine the AE profile for the respective treatment regimens under study. A patient that discontinues APR-246 therapy before completion of Cycle 3 without DLT is considered evaluable for the purpose of safety review by the DRT only if at least 75% of the scheduled doses of APR-246 were administered in Cycles 1 through 3.
 
The study will implement the following stopping criteria:
 
• Any death occurring between receipt of the first dose of APR-246 through 30 days of last dose of study treatment which is not clearly and solely due to underlying disease,• A medically equivalent SAE experienced by >1 patient, which is not clearly and solely due to underlying disease,• A severe AE (NCI-CTCAE toxicity grade >3) experienced by >2 patients that does not return to grade ≤ 1 or baseline within 7 days ,• A grade ≥ 3 neurologic AE that does not return to grade ≤ 1 or baseline within 7 days.

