administered starting at Cycle 8 for up to a total of 24 cycles. Cycle 1 will consist of 35 days. Cycles 2 and beyond will be 28 days. The safety assessment (DLT) period begins at the start of treatment and extends to the end of Cycle 3.

Patients with RT will receive APR-246 administered IV at the assigned cohort dose with standard doses of venetoclax and rituximab. Dose escalation will proceed in a standard 3 + 3 dose escalation design.

The intended three dose levels of APR-246 are: 1.5 g/day, 3.0 g/day, and 4.0 g/day administered as an IV infusion over 6 hours. The dose escalation will proceed until a pharmacologically active dose level is achieved. It will be stopped if the maximum tolerated dose (MTD) is reached at a dose level below the maximum planned dose of 4.0 g/day. For the determination of MTD the following rules will be applied:

- Three patients will be enrolled to Dose Level 1.
- If 0 patients out of 3 experience a DLT at Dose Level 1 (1.5 g/day of APR-246), the dose will advance to the next level (Dose Level 2, 3.0 g/day).
- If 1 of the first 3 patients at Dose Level 1 experiences a DLT, 3 additional patients will be recruited and treated at the same dose level (1.5 g/day of APR 246).
- If ≥ 2 patients out of 3-6 patients in a cohort experience a DLT at Dose Level 1 (1.5 g/day of APR-246), the study will temporarily discontinue enrollment and the Data Review Team (DRT) will consider further enrollment and possible dose/schedule adjustments.
- If < 2 patients out of 6 experiences a DLT at Dose Level 1 (1.5 g/day), dose escalation will proceed to the next cohort level (Dose Level 2, 3.0 g/day).
- For each cohort, if there are 0 DLTs in the first 3 patients enrolled, the cohort will advance to the next level. If there is 1 DLT in the first 3 patients enrolled to a cohort, the cohort will enroll an additional 3 patients. If there are ≥ 2 DLTs in a cohort, the prior lower dose level will be declared the MTD.
- If there are ≤ 1 DLT in the first 3 patients enrolled at Dose Level 3, 4.0 g/day APR-246, the study will enroll 3 additional patients at Dose Level 3. If there are ≤ 1 DLTs in 6 patients enrolled at Dose Level 3, 4.0 g/day APR-246 will be declared the MTD.

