5.1.4 Dose-Limiting Toxicity

All TEAEs are relevant to the determination of DLTs unless they are clearly and solely due to the disease under study. The DLT evaluation period will be up to 91 days (7 days of APR-246 monotherapy plus 84 days for Cycle 1-3 with combination therapy) after the first dose of APR-246 is administered. A DLT is defined as any of the following TEAEs using the National Cancer Institute Common Terminology Criteria for Adverse Events (NCI-CTCAE), as follows:

- Any neurologic toxicity of grade 4
- Any grade ≥ 3 non-hematologic toxicity except for:
 - First occurrence of grade 3 electrolyte abnormalities and/or creatinine CL decrease resolving to grade 2 (or baseline if baseline is grade ≥ 2) within 48 hours with supportive treatment.
 - Grade 3 fatigue, nausea, vomiting, diarrhea or other manageable constitutional symptom(s) that is/are responsive to supportive therapy.
 - Grade 3 infection responding to appropriate antimicrobial therapy.
 - Any neurologic toxicity of grade 3 that does not return to grade ≤ 1 or baseline within 7 days.
- Any grade ≥ 3 hematologic toxicity will be considered a DLT except for:
 - Grade 3 neutropenia without fever
 - Grade 4 neutropenia without fever lasting 8 days or less
 - Grade 3 thrombocytopenia that does not result in bleeding or transfusion
 - Grade 3/4 lymphopenia/lymphocytosis
 - Grade 3/4 WBC decreased
 - Grade 3/4 WBC increased

Any toxicity, regardless of the NCI-CTCAE v5.0 grade, resulting in discontinuation, dose reduction or treatment with less than 75% of planned doses of APR-246 study drug, will be reviewed by the DRT, and will be considered a DLT unless clearly and solely related to the disease under study. The DRT will consist of the Medical Monitor, Site Principal Investigators, and other clinical research personnel that the Sponsor may deem appropriate.

G-CSF support for the management of neutropenia and prophylactic antimicrobial therapy are allowed, including during the DLT period.

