6.0 STUDY EVALUATIONS

6.1 Schedule of Study Evaluations

Study evaluations are summarized in [Table 17](#) and described in Sections [6.2](#) through [6.10](#).

Table 17: Schedule of Assessments

Protocol activities	Screening ^a	APR-246 Lead-In ^b			Cycle 1				Cycles 2 -7				Cycles 8 and Beyond			Cycles 4, 7, 10, 13, 16, 19, 22 and 25 ⁱ	End of Treatment ^p	Follow-up (28 Days after End of Treatment) ^q	
		D1	D2	D3	D1	D2	D8 ^b	D15 ^b	D1 ^c	D2	D8 ^b	D15 ^b	D1 ^c	D8 ^b	D15 ^b	D1			
Informed consent	x																		
Medical history ^d	x																		
Physical examination ^e	x	x			x				x				x					x	
Height ^s	x																		
Weight	x	x			x				x				x					x	
Vital signs ^e	x	x	x		x		x	x	x	x	x	x	x	x	x	x		x	
ECOG PS	x	x			x				x				x					x	
APR-246 (IV) ^f	x				x		x	x	x	x	x	x	x	x	x	x			
APR-246 (PO) ^f		x																	
Venetoclax ^g					Ramp-up Week 1-5				Given PO at a dose of 400 mg daily through Cycle 24										
Rituximab ^h									x										
Disease assessment ⁱ	x																x	x	
Hematology ^j	x	x ^j	x ^j	x ^j	x				x	x		x	x	x	x	x		x	
Serum chemistry ^k	x	x			x			x	x		x	x	x	x	x	x		x	
Creatinine CL ^l	x																		
PD assessments ^u		x	x	x	x	x													
Blood sample for GSH assay (Local Lab) ^v		x	x	x	x														
HCV/HBV test ^t	x																		
Pregnancy test ^m	x																		
ECG ⁿ	x	x	x		x		x	x	x				x					x	
APR-246 PK sample ^o		x	x	x					x		x ^o	x ^o	x						
Clinical toxicity assessment		Starting at the time of informed consent through 30 days after last dose ^r																	
Concomitant medications		Reviewed throughout study																	
Survival																		x	

Footnotes to Schedule of Assessments

- a. All screening/baseline evaluations are performed within 28 days prior to the start of study treatment. In the event that a visit or test cannot be scheduled on the exact visit day, a window of ± 3 days is allowable. Cycle 1 is 5 weeks (35 days) in duration. Subsequent cycles are 28 days in duration.
- b. A window of ± 3 days applies to this study visit.
- c. After the first cycle, Day 1 evaluations of subsequent cycles are to be done within 3 days prior to next cycle drug administration.
- d. Full medical history is obtained at screening for safety and eligibility purposes; this will include any clinically significant findings from 28 days prior to screening date.

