- e. Physical exam and vital signs (including blood pressure, heart rate, respiration rate and temperature) are completed for safety purposes and clinically significant items are recorded as AEs where appropriate. Vital signs are collected prior to APR-246 infusion, 2 hours into infusion and at EOI (± 30 minutes at all time points). On Day 2 of the APR-246 monotherapy lead-in period, vital signs are collected prior to PO administration of APR-246, and then 2 hours and 6 hours after APR-246 administration. For patients with palpable lymphadenopathy and/or organomegaly, 2 dimensional measurements of lymph nodes and measurements of liver/spleen size (below costal margin) may be included as part of each physical examination as clinically indicated.
- f. Study treatment will consist of APR-246 at assigned dose level administered once weekly, on Days 1, 8 and 15 of each 28-day cycle. On Day 2 of the monotherapy lead-in period, a single dose of APR-246 will be administered PO.
- g. Venetoclax is given PO at the dose of 20 mg during Week 1, 50 mg during Week 2, 100 mg during Week 3, 200 mg during Week 4, and 400 mg during Week 5 and thereafter. Each dose should be given once daily at approximately the same time every day, with a meal and water. At the discretion of the treating Investigator, patient may be hospitalized prior to administration of the first dose of venetoclax (20 and 50 mg) and continuing for 24 hours after.
- h. Rituximab will be initiated IV, following the 5-week venetoclax dose ramp-up, at 375 mg/m^2 on Cycle 2, Day 2 ($+3$ days) and 500 mg/m^2 on Day 2 ($+3$ days) of Cycles 3-7. After 6 cycles of treatment with APR-246 + venetoclax + rituximab, APR-246 and venetoclax will continue to be administered in Cycle 8 and beyond for up to 24 cycles.
- i. Responses will be assessed every 3 cycles starting at Cycle 4 on Day 1 (± 7 days) according to Lugano response criteria via PET/CT imaging, blood, and BM. For patients who achieve CR, imaging may be omitted, and MRD assessment will be completed using flow cytometry and/or molecular techniques.
- j. Hematology must include complete blood count with differential. Hematology test should be completed before and after APR-246 administration on Days 1 and 2 of the APR-246 monotherapy lead-in period, Day 3 of the lead-in period, and on Day 1 of Cycle 1 before and approximately 4 hours after APR-246 administration.

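### The DLT window is totalled as up to 91 days, but the lead-in plus Cycles 1-3 that it names lasts 98 days with the stated 35-day Cycle 1

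*Combined protocol and SAP*

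**What the plan says.** Section 5.1.4 and the synopsis (Definition of DLT) both count the window from the first APR-246 dose and limit it to "up to 91 days (7 days of APR-246 monotherapy plus 84 days for Cycle 1-3 with combination therapy").

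Two other places define the same window by cycles:

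- Synopsis, Treatment Plan: "The safety assessment (DLT) period will occur in the monotherapy lead-in and throughout Cycles 1, 2, and 3 of combination treatment".
- Section 4.1: "The safety assessment (DLT) period begins at the start of treatment and extends to the end of Cycle 3".

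Three places give the cycle lengths, and they agree on Cycle 1:

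- Section 4.1: "Cycle 1 will consist of 35 days. Cycles 2 and beyond will be 28 days".
- Figure 1: "Cycle 1: D1-35 APR-246 IV Dose X D1, 8, 15".
- Table 17, footnote a: "Cycle 1 is 5 weeks (35 days) in duration. Subsequent cycles are 28 days in duration".

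The one contrary phrase is in footnote f of Table 17, where APR-246 is "administered once weekly, on Days 1, 8 and 15 of each 28-day cycle".

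Section 5.1.4 adds that events meeting the criteria after the evaluation period are not DLTs. It also ties evaluability of a patient who stops early to the share of APR-246 doses given in Cycles 1 through 3.

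**The concern.** The day count and the cycle definition describe the same period but end about a week apart. "Up to" does not remove the conflict: a ceiling of 91 days is shorter than the periods it itemises. Read literally, the ceiling drops roughly the last week of Cycle 3, and an event there changes status depending on which sentence is applied.

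That matters because the 3+3 rules in Section 4.1 turn on one or two DLTs, and Section 5.1.5 defines the MTD by the number of patients with a DLT in the safety assessment period. One event counted or not counted can change an escalation step or the MTD.

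The documents also do not say which boundary governs when a cycle is delayed. Section 5.2 sets no general requirement to consult the Medical Monitor for holds of up to 4 weeks, so the two boundaries could end up much further apart than a week.

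**Working it through.** **Reproducing the stated figure.** With 28-day cycles throughout, 3 × 28 = 84 and 7 + 84 = 91. The protocol's total therefore reproduces only if Cycle 1 is 28 days.

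**Using the stated cycle lengths.** Inputs: lead-in 7 days (Section 4.1), Cycle 1 35 days, Cycles 2 and 3 28 days each (Section 4.1; Table 17 footnote a).

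- Cycles 1-3: 35 + 28 + 28 = 91 days, not 84.
- Lead-in plus Cycles 1-3: 7 + 91 = 98 days.

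Cycles 1-3 alone do come to 91, but the text counts the lead-in inside the 91 and gives the cycles 84.

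**Calendar on the planned schedule** (first APR-246 dose = study day 1).

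| Event | Study day |
|---|---|
| Cycle 1 Day 1 | 8 |
| Cycle 2 Day 1 | 43 |
| Cycle 3 Day 1 | 71 |
| Cycle 3 Day 2 (rituximab) | 72 |
| Cycle 3 Day 15 (last APR-246 infusion of Cycle 3) | 85 |
| Cycle 3 Day 21 | 91 |
| Cycle 3 Day 28 | 98 |

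The disputed days are 92-98, or six days if 91 days after the first dose is read as ending on study day 92. All planned APR-246 infusions through Cycle 3 fall by day 85 (day 88 with the +3-day window), so the 75% dose rule is unaffected. A cumulative shift of more than 91 − 85 = 6 days would move the last infusion past day 91.

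**Size of the effect on the 3+3 outcome.** The documents give no DLT rate or timing, so I assume a 98-day DLT risk R, equal at every level. The daily hazard is h = −ln(1 − R)/98. The chance that a patient's first DLT falls in the disputed week is exp(−91h) × [1 − exp(−7hf)], where f is the hazard in that week relative to the earlier hazard. With f = 1 this is 0.0035, 0.0068, 0.0129 and 0.0194 for R = 0.05, 0.10, 0.20 and 0.33.

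Let q be the probability of no DLT in the window. Under the Section 4.1 rules:

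- Levels 1 and 2: P(pass) = q³ + 3(1 − q)q⁵.
- Level 3: P(pass) = q⁶ + 6(1 − q)q⁵.

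A level passed on the 98-day count is always passed on the 91-day count for the same patients. Let s be the 98-day pass probability at Levels 1 and 2, d the 91-day minus 98-day difference there, and d₃ the difference at Level 3. Then P(outcomes differ) = d + s·d + s²·d₃. A pause at Level 1 is treated as the end, with no replacements or expansion patients.

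| R | Pass Level 1 or 2, 91 v 98 days (f = 1) | Pass Level 3, 91 v 98 days (f = 1) | Outcomes differ, f = 1 | f = 0.5 | f = 0.25 |
|---|---|---|---|---|---|
| 0.05 | 0.977 v 0.973 | 0.971 v 0.967 | 1.06% | 0.52% | 0.26% |
| 0.10 | 0.917 v 0.906 | 0.899 v 0.886 | 3.16% | 1.58% | 0.79% |
| 0.20 | 0.736 v 0.709 | 0.687 v 0.655 | 6.32% | 3.22% | 1.62% |
| 0.33 | 0.473 v 0.434 | 0.398 v 0.358 | 6.26% | 3.26% | 1.66% |

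The last three columns use unrounded pass probabilities. A simulation of 200,000 trials per setting agreed to within 0.1 percentage point. Whenever the outcomes differ, the 91-day count gives the higher dose level.

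**Delay.** If a 28-day hold in Cycle 1 or 2 shifts every later visit (an assumption), Cycle 3 runs from study day 71 + 28 = 99 to 98 + 28 = 126, wholly outside a literal 91-day count.

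**The case against.** The best reply is that the intent is clear. Every statement of the window names the lead-in plus Cycles 1-3, and the evaluability rule uses the same cycles, so 84 is probably just a wrong subtotal. Harm then requires the Data Review Team to enforce that total over the explicit end of Cycle 3. This is fair, and the percentages above are conditional on such enforcement. But the wrong number sits in the operative DLT definition, and nothing says which statement prevails.

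The percentages also rest on invented rates, and constant hazard is the least apt case: no APR-246 or rituximab dose is planned on days 92-98, although daily venetoclax continues. The reduced-hazard columns are the more plausible ones.

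The delay scenario is weaker still. Section 5.3.2.3 and the renal and hepatic parts of Table 10 omit doses, which need not move the calendar, while Table 10 delays the dose for other toxicities. If doses are omitted, a 28-day hold starting at Cycle 1 Day 1 or at any Cycle 2 infusion loses 3 of the 9 infusions in Cycles 1-3, leaving 67%. If toxicity caused the hold, Section 5.1.4 already treats less than 75% of planned doses as a DLT unless the cause is solely the disease. Holds starting at Cycle 1 Day 8 or Day 15 lose 2 of 9, leaving 78%, and escape that rule. Tables 5 and 6 also require Medical Monitor consultation in some situations regardless of the length of the hold.

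Finally, late events are still reported and reviewed, the Section 8.4 stopping criteria do not use this window, and Section 5.1.5 selects the recommended dose by apoptosis at or below the MTD or maximum dose. All of this limits the consequence; none of it makes 91 equal 98.

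**Conclusion.** The concern holds: the window is wrong as written, and it should be fixed. The contradiction follows from the protocol's own cycle lengths and needs no assumption: 91 days stated, 98 days for the periods named.

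The practical effect is modest and confined to the escalation step and the MTD ceiling. If the 91-day limit is applied literally on an undelayed schedule, the dose-level outcome changes in about 0.3% to 3.3% of trials with reduced hazard in the last week and 1.1% to 6.3% with constant hazard, always toward the higher level. These figures depend on assumed DLT risks of 5% to 33%, equal across levels. Delayed cycles could widen the gap, but by how much depends on whether holds shift the calendar, which the documents leave mixed.

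**What to change.** Reconcile the synopsis (Treatment Plan and Definition of DLT), Section 4.1 and Section 5.1.4 to one DLT window whose day count agrees with the stated cycle lengths. If the end of Cycle 3 is intended, the sum is 7 + 35 + 28 + 28 = 98 days. If 91 days is intended, the wording that runs the period through Cycle 3 and the 84-day allocation must change. Which is meant is for the sponsor to decide.

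State also whether the day count or completion of Cycle 3 governs when a cycle is delayed, and from which day the count starts. As a separate tidy-up, reconcile Table 17 footnotes a and f on cycle length.

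The cost is wording only. On the planned schedule it adds at most about one week to each cohort decision, and nothing if 91 days is meant.
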